6.6 Pregnancy

All pregnancies and outcomes of pregnancy should be reported to AstraZeneca during the course of the study (including the continued access) and within 6 weeks of the last dose of AZD9291.

6.6.1 Maternal exposure

If a subject becomes pregnant during the course of the study investigational product should be discontinued immediately.

Pregnancy itself is not regarded as an adverse event unless there is a suspicion that the investigational product under study may have interfered with the effectiveness of a contraceptive medication. Congenital abnormalities/birth defects and spontaneous miscarriages should be reported and handled as SAEs. Elective abortions without complications should not be handled as AEs. The outcome of all pregnancies (spontaneous miscarriage, elective termination, ectopic pregnancy, normal birth or congenital abnormality) should be followed up and documented even if the subject was discontinued from the study.

If any pregnancy occurs in the course of the study or within 28 days of the final dose of the investigational product, then the Investigator or other site personnel informs the appropriate AstraZeneca representatives within 1 day ie, immediately but **no later than 24 hours** of when he or she becomes aware of it.

The designated AstraZeneca representative works with the Investigator to ensure that all relevant information is provided to the AstraZeneca Patient Safety data entry site within 1 or 5 calendar days for SAEs (see Section 6.4) and within 30 days for all other pregnancies.

The same timelines apply when outcome information is available.

6.6.2 Paternal exposure

Pregnancy of the subject's partners is not considered to be an adverse event. However, the outcome of all pregnancies (spontaneous miscarriage, elective termination, ectopic pregnancy, normal birth or congenital abnormality) should if possible be followed up and documented. To capture information about a pregnancy from the partner of a male subject, the male subject's partner consent must be obtained to collect information related to the pregnancy and outcome; the male subject should not be asked to provide this information. A consent form specific to this situation must be used. The outcome of any conception occurring from the date of the first dose until 4 months after dosing should be followed up and documented.

6.7 Management of Investigational Product related toxicities

If a patient experiences a CTCAE grade 3 or higher and/or unacceptable toxicity (any grade) not attributable to the disease or disease-related processes under investigation, where the Investigator considers the AE of concern to be specifically associated with AZD9291, dosing will be interrupted and supportive therapy administered as required in accordance with local practice/guidelines.

If the toxicity resolves or reverts to \leq CTCAE grade 2 within 3 weeks of onset, treatment with AZD9291 may be restarted at the same dose (80 mg) or a lower dose (40 mg) using the rules below for dose modifications (Table 7) and with discussion and agreement with the AstraZeneca Study Physician as needed. There will be no individual modifications to dosing schedule in response to toxicity, only potential dose reduction or dose interruption.

If the toxicity does not resolve to \leq CTCAE grade 2 after 3 weeks, then the patient should permanently discontinue the study treatment and be observed until resolution of the toxicity.

Table 7 Dose interventions

Intervention	AZD9291 Dose
Starting Dose	80 mg
Reduced Dose -1	40 mg

On resolution of toxicity within 3 weeks:

- If an AE subsequently requires dose interruption, AZD9291 may restart at the same dose or the reduced dose, on resolution/improvement of the AE at the discretion of the Investigator.

If new or worsening pulmonary symptoms (eg, dyspnoea) or radiological abnormality suggestive of interstitial lung disease is observed, an interruption in study treatment dosing is recommended, and the AstraZeneca study physician should be informed. A questionnaire regarding the results of the full diagnostic workup (including high-resolution computed tomography (HRCT), blood and sputum culture, haematological parameters) will be sent to Investigators. It is strongly recommended to perform a full diagnostic workup, to exclude alternative causes such as lymphangitic carcinomatosis, infection, allergy, cardiogenic edema, or pulmonary hemorrhage. In the presence of confirmatory HRCT scans where other causes of respiratory symptoms have been excluded, a diagnosis of interstitial lung disease should be considered and study treatment permanently discontinued.

In the absence of a diagnosis of interstitial lung disease study treatment may be restarted following consultation with the AstraZeneca Study Physician.

Patients with QTcF prolongation to >500 msec should have study treatment interrupted and regular ECGs performed until resolution to <481 msec or recovery to baseline if baseline

QTcF is ≥ 481 msec; and then restart at a reduced dose of 40mg. If there are signs/symptoms of serious arrhythmia, or if the toxicity does not resolve to grade ≤ 1 (i.e. QTcF < 481 msec), or to baseline QTcF within 21 days, the patient will permanently discontinue the study treatment.

Patients experiencing any of the following will not be permitted to restart study treatment:

- Corneal ulceration
- Interstitial Lung Disease (ILD)
- QTc interval prolongation with signs/symptoms of serious arrhythmia

6.7.1 Skin reactions

Recommendations for appropriate management of skin reactions, including guidance on dose-adjustments for clinically significant and/or intolerable skin reactions that are considered by the investigator to be causally related to AZD9291 will be provided to investigators.

Skin reactions are to be reported as AEs in the CRF, with additional details captured in the "SKNREAC" CRF:

- Changes in the characteristics of skin reactions will be collected in the "SKNREAC" CRF.
- Changes in the CTCAE grade of skin reactions will be collected in the AE CRF.

Photographs of skin reactions may be collected and these photographs should be available for central review by AstraZeneca and for external expert dermatological review if required.

Skin biopsies of skin reactions may be taken as per investigator discretion, as per the standard local medical practice. Skin biopsies should ideally be taken in subjects with clinically significant or grade ≥ 3 skin reaction.

6.7.2 Diarrhoea

Recommendations for appropriate management of diarrhoea, including dose-adjustments for adverse events of diarrhoea that are of CTCAE grade ≥ 3 or that are clinically significant and/or intolerable and considered by the investigator to be causally related to AZD9291, will be provided to investigators. Changes in CTCAE grade of diarrhoea will be captured in the AE eCRF.

6.8 Study governance and oversight

6.8.1 Steering Committee

A Steering Committee comprising of the principal investigators for study D5160C00017 in addition to principal investigators from the other AZD9291 pivotal studies will provide advice on any aspect of the study design or conduct based on requests from the sponsor and assure consistency across the entire AZD9291 pivotal programme.

No Data Monitoring Committee (DMC) is planned, as this study is an open-label non-randomised phase II study. In addition the safety profile of AZD9291 from the ongoing phase 1 trial in a similar NSCLC patient population is modest, predictable with no reported life-threatening adverse events. There is therefore no requirement for pre-planned specified expert independent safety reviews in this study.

7. INVESTIGATIONAL PRODUCT AND OTHER TREATMENTS

7.1 Identity of investigational product(s)

Investigational product	Dosage form and strength	Manufacturer
AZD9291	40-80 mg Tablets	AstraZeneca

7.2 Dose and treatment regimens

AstraZeneca will supply AZD9291 as tablets for oral administration as a single daily dose of 80 mg. AZD9291 can be taken with or without food at the same time each day. Patients will be required to fast (water only) for at least 8 hours prior to the collection of a fasting glucose sample as per the study plan (Table 1 and Table 2) and Section 5.2.1.

At each dispensing visit, sufficient AZD9291 for 21 days treatment, plus overage, will be dispensed. Prior to the final DCO, individual bottles will be dispensed in accordance with the medication identification numbers provided by the IVRS/IWRS. Dispensing of study treatment post final DCO will be completed outside of IVRS/IWRS.

Patients should swallow one AZD9291 80 mg tablets once daily, commencing on Cycle 1 Day 1. Tablets should be taken whole with water.

The initial dose of AZD9291 can be reduced under circumstances described in Section 6.7.

Doses should be taken approximately 24 hours apart at the same timepoint each day. On ctDNA sampling days, the doses should be delayed until instructed to take by site personnel. Doses should not be missed. If a patient misses taking a scheduled dose, within a window of 12 hours, it is acceptable to take the dose. If it is more than 12 hours after the dose time, the missed dose should not be taken, and patients should be instructed to take the next dose at the next scheduled time. If a patient vomits after taking their AZD9291, they should not make up for this dose, but should take the next scheduled dose.

Prior to the final DCO, any change from dosing schedule, dose interruptions, dose reductions should be recorded in the eCRF. Post the final DCO, drug accountability information will be stored in medical records at site.

Tablets will be packed in high-density polyethylene (HDPE) bottles with child-resistant closures. Bottles will be dispensed to subjects in the AstraZeneca packing provided. The

packaging includes bottles, caps and a label. Bottle tampers should not be broken prior to dispensing study drug to a patient.

Additional information about the Investigational product may be found in the Investigators' Brochure.

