Echocardiogram/MUG A	X		← every 12 weeks(±1 week) relative to first dose →										5.2.5
Plasma sample for ctDNA ^g	X ⁱ	X	X	X	X	X	X		← every 6 weeks in line with RECIST assessments ^j →			4.3.3 & 5.6.2	
Optional genetic consent and sample	X ^k												5.5
Optional CSF sample					X (once only) ^l								5.4.1

Table 1 Study Plan - Prior to 24 months post LSFD

Visit	Screening	Treatment Period (further treatment cycles as per Cycle 7)							Treatment Discontinuation	Follow-up Period			For details see Protocol Section
	1	2	3	4	5	6	7-9	10+		28-day follow-up	Progression follow-up	Survival follow-up	
Cycle ^a / Day		C1 D1	C1 D8	C1 D15	C2 D1	C3 D1	C4-6 D1	C7 ^b +D1	NA	NA	NA	NA	
Day	-28 to 1	1	8	15	22	43	64-106	127+	NA	NA	NA	NA	
Window (days) ^z	NA	0	±2	±2	±7	±7	±7	±7	0	±7	±7	±7	SECTION:
Tumour assessments (RECIST v1.1) ^m	X ^v	every 6 weeks(±1 week) relative to first dose until disease progression 										4.2 & 5.1.1	
EORTC QLQ-C30 and EQ-5D-5L (by electronic device)		X ^g	every 6 weeks(±1 week) relative to first dose 					X		X ⁿ	X ⁿ	5.3.2.1 & 5.3.2.2	
EORTC QLQ LC13 (by electronic device)		X ^g	Weekly(±2days) relative to first dose 		every 3 weeks(±3 days) relative to first dose 			X		X ^o	X ^o	5.3.2.1	
PRO-CTCAE (by electronic device) ^p		X ^g	weekly(±2 days) for first 18 weeks of treatment 				X ^q	X		X ^o	X ^o	5.3.2.3	
Healthcare Resource Use												5.3.2.5	
Dispense study medication		X			X	X	X	X ^b					3.3 & 7.2

Table 1 Study Plan - Prior to 24 months post LSFD

Visit	Screening	Treatment Period (further treatment cycles as per Cycle 7)							Treatment Discontinuation	Follow-up Period			For details see Protocol Section
	1	2	3	4	5	6	7-9	10+		28-day follow-up	Progression follow-up	Survival follow-up	
Cycle ^a / Day		C1 D1	C1 D8	C1 D15	C2 D1	C3 D1	C4-6 D1	C7 ^b +D1	NA	NA	NA	NA	
Day	-28 to 1	1	8	15	22	43	64-106	127+	NA	NA	NA	NA	
Window (days) ^z	NA	0	±2	±2	±7	±7	±7	±7	0	±7	±7	±7	SECTION:
Dose with AZD9291		← Daily dosing →											7.2
Concomitant medication & procedures		← →											7.7
Adverse events ^w		← →									X ^t	X ^t	6.3 & 6.4
Survival Status												X ^s	4.3.4
Anti-cancer treatment	X										X	X ^s	4.3.3, 4.3.4
Subsequent response /progression data												X ^t	5.8

^a A cycle is defined as 21-day treatment period.

^b Visit schedule changes after Cycle 7 Day 1 from every 21 days (3 weeks) to every 42 days (6 weeks).

^c Consent may be taken prior to 28-day window if required,

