
^t Record subsequent response/progression data every 6 weeks until first confirmed disease progression on a subsequent treatment.

^u Discontinuation biopsy can be taken at discontinuation or progression, whichever comes first

^v If the patient has received CT/MRI scan before signing the ICF, and within 28 days prior to treatment, the assessment can still be acceptable if the scan meets the RECIST 1.1 criteria.

^w A photograph with proper identification cover may be taken by site and shared with Sponsor if the patient has a rash, or changes to eyelashes, skin or eyes during the study.

^x For patients participating biomarker/genetic research and from outside of China, HBV and HIV tests are needed for sample shipment purpose, and results should be negative.

^y Fasting glucose during Cycle 1 only (3 visits, C1D1, D8 and D15). And from cycle 2 onwards (visit will occur only on Day 1 for each cycle) random glucose will be collected

^z Visit windows are always calculated in relation to Cycle 1, Day 1.

Table 2 Study Plan - After 24 months Post LSFD until Final DCO^a

Visit	Treatment post 24 months every 84 days (12 weeks)	Treatment Discontinuation	Follow-up Period			For details see Protocol Section
	10+		28-day follow-up	Progression follow-up	Survival follow-up	
Cycle ^b / Day	D1	NA	NA	NA	NA	
Window (days)	±7	0	±7	±7	±7	SECTION:
Optional tumour biopsy for exploratory research		X		X		5.6
Physical examination, including weight	X	X				5.2.3 & 5.2.6.2
WHO Performance status	X	X				4.1
Pregnancy test (pre-menopausal females only)	as clinically indicated					5.2.1
Ophthalmologic assessment	← as clinically indicated →					5.2.7.1
Vital signs ^c	X					5.2.6
Digital ECG	X	X				5.2.4
Echocardiogram/MUGA	← every 12 weeks (±1 week) related to first dose →					5.2.5
Clinical chemistry/ Haematology/Urinalysis ^c	X	X				5.2.1
Echocardiogram/MUGA	X					5.2.5
Plasma sample for ctDNA ^c	X					4.3.3 & 5.6.2

Table 2 Study Plan - After 24 months Post LSFD until Final DCO^a

Visit	Treatment post 24 months every 84 days (12 weeks)	Treatment Discontinuation	Follow-up Period			For details see Protocol Section
	10+		28-day follow-up	Progression follow-up	Survival follow-up	
Cycle ^b / Day	D1	NA	NA	NA	NA	
Window (days)	±7	0	±7	±7	±7	SECTION:
Optional genetic consent and sample	X ^d					5.5
Optional CSF sample	X (once only) ^e					5.4.1
Tumour assessments (RECIST v1.1)	← X (every 12 weeks until disease progression) ^f →					4.2 & 5.1.1

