4.2 Treatment period

A cycle of treatment is defined as 21 days of once daily AZD9291 treatment. After Cycle 7 Day 1, the duration between study visits will change from every 21 days (3 weeks) to every 42 days (6 weeks).

If a patient continues to receive treatment with AZD9291 beyond RECIST 1.1 defined progression they must continue to follow the Treatment visit schedule and assessments excluding study specific RECIST 1.1 assessments.

Descriptions of the procedures for this period are included in the Study Plan (see Table 1 and Table 2).

After final DCO (i.e. after final data cut-off date), patients may continue to receive AZD9291, if in the opinion of their treating physician they are continuing to derive clinical benefit from continued treatment, the period is defined as continued access. (see Section 4.4 and Section 7.8)

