7.5 Compliance

The administration of all study drugs should be recorded in the appropriate sections of the Case Report Form.

Patients should return all unused medication and empty containers to the investigator.

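### Section 7.2 dispenses 21 days of drug at every dispensing visit, but after Cycle 7 Day 1 those visits are 42 days apart

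*Protocol*

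**What the plan says.** Section 7.2 of the protocol gives the dispensing rule: "At each dispensing visit, sufficient AZD9291 for 21 days treatment, plus overage, will be dispensed". It gives no size for the overage and does not distinguish early from late visits. The same section has patients take one 80 mg tablet daily and adds "Doses should not be missed".

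Table 1 (section 4) marks dispensing on Day 1 of Cycles 1 to 6 and at Cycle 7 onwards. The last of these cells carries footnote b: "Visit schedule changes after Cycle 7 Day 1 from every 21 days (3 weeks) to every 42 days (6 weeks"). Section 4.2 gives the same change of visit interval, without mentioning dispensing. Footnote a of Table 1 states: "A cycle is defined as 21-day treatment period".

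Two further provisions bear on how far a supply can stretch. On visit timing, footnote z of Table 1 says "Visit windows are always calculated in relation to Cycle 1, Day 1"; the windows for the Day 1 visits from Cycle 2 onwards are ±7 days. On leftover tablets, section 7.5 says "Patients should return all unused medication and empty containers to the investigator", without saying when.

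**The concern.** The quantity in section 7.2 and the dispensing schedule in Table 1 agree only while visits are 21 days apart. From Cycle 7 Day 1 the interval doubles and the stated quantity does not. A site that follows section 7.2 literally hands over half of the tablets needed to reach the next visit, before overage. A site that hands over 42 days' supply departs from the section's wording. Section 7.6 requires study drug to be used only as the protocol directs, and section 9.2 has monitors check protocol adherence and drug accountability, so the wording matters to sites.

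The patients concerned are all those still on drug after Day 127, and treatment has no maximum duration. What is at stake is continuity of daily dosing in these patients, not the statistical design.

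**Working it through.** **Inputs**

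- Supply per dispensing visit: 21 + k days, where k is the overage (section 7.2). The protocol does not state k.
- Consumption: one tablet per day (section 7.2).
- Visit interval: 21 days up to Cycle 7 Day 1, then 42 days (Table 1 footnote b; section 4.2).
- Cycle 7 Day 1: 1 + 6 × 21 = Day 127 (agrees with Table 1). Next visit: 127 + 42 = Day 169.

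**Plan's own figure.** On the early schedule, need = 21 days and supply = 21 + k days. The rule works there.

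**Range for k.** With ±7-day windows anchored to Cycle 1 Day 1, the widest gap between two 21-day visits is 21 + 14 = 35 days, so the early schedule justifies at most 35 − 21 = 14 days of overage. I therefore take k from 0 to 14 as an assumption.

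**After Cycle 7 Day 1, visits on time, no carry-over of tablets**

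Shortfall = 42 − (21 + k). First uncovered day = 127 + 21 + k.

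| Assumed k (days) | Days covered | Coverage | Shortfall (days) | First gap |
|---|---|---|---|---|
| 0 | 21 of 42 | 50% | 21 | Day 148 to 168 |
| 7 | 28 of 42 | 66.7% | 14 | Day 155 to 168 |
| 14 | 35 of 42 | 83.3% | 7 | Day 162 to 168 |

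To cover an on-time 42-day interval, k must be 21, which is 100% of the nominal supply. With the same ±7-day windows the widest 42-day interval is 42 + 14 = 56 days, which would need k = 56 − 21 = 35.

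**If patients keep every leftover tablet and all visits are on time**

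Six dispensings before Day 127 leave a stock of 6k. The first n 42-day intervals are covered if 6k + n(21 + k) ≥ 42n, that is, k ≥ 21n/(6 + n).

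- k = 7: stock 42, falling by 42 − 28 = 14 per interval, so it is exhausted after 3 intervals. The fourth starts on Day 127 + 126 = 253 with 28 tablets, and the gap is Day 281 to 294.
- k = 14: stock 84, falling by 42 − 35 = 7 per interval, so it is exhausted after 12 intervals. The thirteenth starts on Day 127 + 504 = 631 with 35 tablets, and the gap is Day 666 to 672.

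Carry-over delays the gap but does not remove it.

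**Table 2 (provisional).** The column heading reads "Treatment post 24 months every 84 days (12 weeks"), and dispensing is marked there too. Before overage that would leave 84 − 21 = 63 days uncovered. Table 2's footnotes are not in the text reviewed and may address dispensing, so this is not relied on.

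**The case against.** The best defence is that 21 days is simply one treatment cycle and section 7.2 was meant per cycle. The protocol keeps cycle-based wording elsewhere despite the 42-day visits, for example for ECGs (section 5.2.4) and weight (section 5.2.6.2). Bottles are assigned by IVRS/IWRS until the final data cut-off, and a sensibly configured system would issue enough for 42 days. A site that reads the footnote on the dispensing row together with the instruction not to miss doses would expect the same. Pack size, overage and system settings are not in the protocol, so no shortage can be inferred. The dated gaps depend on assumed overage, punctual visits and, in the later cases, full retention of tablets.

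Most of this stands as a limit on consequence. The only comparison that comes directly from the text is 21 days against 42; the dated gaps are illustrations. The per-cycle reading is plausible, but the sentence is written per dispensing visit, and the two stop coinciding after Cycle 7 Day 1. Overage does not rescue it either: the most that the early visit windows justify is 14 days, against 21 needed even when the 42-day visit is on time.

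**Conclusion.** The inconsistency holds. Before overage, the stated quantity covers half of each 42-day dispensing interval, and it suffices without carry-over only if the unquantified overage reaches 21 days. The 7- to 21-day range of first-interval shortfalls rests on an assumed overage of 0 to 14 days, on-time visits and no carry-over.

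Severity is minor. The rule is wrong as written, but whether any patient ran short depends on IVRS/IWRS settings that are not shown. Sample size, precision, endpoint definitions and the analysis of ORR, PFS and DoR are not shown to be affected.

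**What to change.** Replace the dispensing sentence in section 7.2 with wording tied to the schedule, for example: *Each dispensing will supply enough AZD9291 for the days until the next scheduled dispensing visit, plus overage for the visit window.* Put this way, it holds for 21-day and 42-day visits and, if Table 2 is confirmed, for 84-day visits, without naming a number.

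Confirm that the IVRS/IWRS dispensing configuration matches. The cost is one sentence of protocol text and one configuration check.

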7.3 Labelling

Labels will be prepared in accordance with Good Manufacturing Practice (GMP) and local regulatory guidelines. The labels will fulfil GMP Annex 13 requirements for labelling. Label text will be translated into local language.

7.4 Storage

All study drugs should be kept in a secure place under appropriate storage conditions. The investigational product label on the bottle specifies the appropriate storage.

7.5 Compliance

The administration of all study drugs should be recorded in the appropriate sections of the Case Report Form.

Patients should return all unused medication and empty containers to the investigator.

7.6 Accountability

The study drug provided for this study will be used only as directed in the study protocol.

The study personnel will account for all study drugs dispensed to and returned from the subject.

The study personnel at the investigational site will account for all drugs dispensed and for appropriate destruction. Certificates of delivery and destruction should be signed.

7.7 Concomitant and other treatments

Information on any treatment in the 4 weeks prior to starting study treatment and all concomitant treatments given during the study, with reasons for the treatment, will be recorded in the Case Report Form (CRF). Guidance on medications that require close monitoring is given in Section 3.5 and [Appendix E](#)

Prohibited Medication/Class of drug:	Usage:
Other anticancer agents, investigational agents and radiotherapy	Should not be given while the patient is on study treatment.

Rescue/Supportive Medication/Class of drug:	Usage:
Pre-medication will be allowed after, but not before the first dose of study treatment.	To be administered as directed by the investigator. This includes management of diarrhoea, nausea and vomiting.
Blood transfusions	Allowed at any time during the study.
Granulocyte colony stimulating factors	Should not be used prophylactically during Cycle 1. Use of prophylactic colony stimulating factors may be considered after Cycle 1 following discussion with the AstraZeneca Study Team Physician.
Corticosteroids and/or bisphosphonates	Patients may receive treatment with corticosteroids and/or bisphosphonates for the treatment of bone metastases.
Palliative radiation	Patients may receive radiotherapy for painful bony metastases.
Supportive care and other medications that are considered necessary for the patient's well-being	To be administered as directed by the investigator.

